4.9 Normal tissue contouring guidelines

Normal tissues will be outlined as solid structures, including the rectum, bladder and femoral heads. The penile bulb will be outlined as a reference structure. No constraints will be placed on the penile bulb, but doses will be recorded. The rectum will be outlined from the anterior flexion of the rectosigmoid superiorly to the ischial tuberosities inferiorly. The bladder

and contents will be contoured. The femoral heads should be outlined down to the region between the greater and lesser trochanters.

The potential bowel space within 5 cuts of the CTV (CTV1 or CTV2, whichever is most superior) should be outlined to minimize dose to the bowel. The potential bowel space includes the areas on either side of the bladder medially.

4.10 CTV/PTV Planning and Constraints

Primary CTV1/PTV1 Planning: The CT and MRI simulation scans will be loaded into a planning computer and fused based on the fiducial markers. At each slice level, the pelvic bones, bladder, rectum, prostate, and seminal vesicles will be outlined. The rectum will be outlined from the anterior flexion of the rectosigmoid superiorly to the ischial tuberosities inferiorly. The entire bladder will be outlined. The femoral heads should be outlined down to the region between the greater and lesser trochanters. As described above, the GTV will include the multiparametric MRI-defined lesion(s). The LEAD RT region will be located as close to the center of the GTV region and should be positioned ≥ 2 mm from the rectum to avoid excessive dose to the rectum.

The primary Clinical Target Volume (CTV1) will include the prostate (with GTV) and the proximal seminal vesicles (usually about 10 mm and/or $\leq 50\%$). The CTV1 may include an extra 1-2 mm beyond the GTV in regions of known bulky disease and/or extracapsular extension as determined by the diagnostic biopsy information and/or MRI. The Planning Target Volume (PTV1) will be 3-5 mm around the CTV1 in all dimensions. For tumors at the base, a margin of 5 mm on the proximal seminal vesicles is recommended.

Constraints: The plans will be evaluated by dose-volume histogram analysis based on prior established criteria.⁹¹ The goal is to obtain these constraints for the combined LEAD plus standard fractionation treatments.

- *Rectum:* Less than or equal to 17% and 35% of the rectum should receive ≥ 65 Gy and ≥ 40 Gy, respectively, in calculated 2 Gy equivalent doses.¹
- *Bladder:* Less than or equal to 25% and 50% of the bladder should receive ≥ 65 Gy and ≥ 40 Gy, respectively, in calculated 2.0 Gy equivalent doses.
- *Small/Large Bowel:* The potential bowel space limits are in terms of absolute volume. ≤ 150 cc of potential bowel space should receive ≥ 45 Gy. A violation will be noted if > 150 cc to 250 cc of potential small bowel space receives ≥ 45 Gy. A violation is if > 250 cc receives ≥ 45 Gy.
- *PTV:* At least 95% of the PTV should receive the prescription dose of 76 Gy in 38 fractions (a minor variation will be $< 95\%$ to $\geq 90\%$ of the prescription dose); a violation would be $< 90\%$. Assuming an α/β ratio of 3.0, the biologically equivalent dose in 2.0 Gy fractions to the LEAD RT region would be 149 Gy.

The maximum dose heterogeneity in PTV1 will be affected substantially by LEAD RT. High dose gradients are acceptable as long as the normal tissue constraints are met.

4.11 Distal seminal vesicle and pelvic lymph node CTV2 and PTV2 for selected high risk patients

A secondary Clinical Target Volume (CVT2) may be treated in selected high risk patients at the discretion of the treating physician. The CTV2 will include the distal seminal vesicles and the pelvic lymph nodes. The PTV2 will be 0 mm. The recommended volumes are on the RTOG website under the "Core Lab/Contouring Atlases" menu (<http://www.rtog.org/CoreLab/ContouringAtlases/ProstatePelvicLymphNodes.aspx>). PTV2 should receive 56.24 Gy at 1.48 Gy per fraction over the 38 fractions of the standard

fractionation treatment. At least 95% of the PTV should receive the prescription dose (a minor variation will be <95% to \geq 90% of the prescription dose); a violation would be <90%. The maximum dose heterogeneity in the PTV2 will be affected by the proximity of CTV1 and possibly LEAD RT. Therefore, no heterogeneity limits are defined.

4.12 Protein biomarkers and immune activation markers in the serum/whole blood

We will assess protein biomarkers and immune activation markers in the serum/whole blood samples of patients receiving high-dose LEAD RT. Samples taken from subjects will be analyzed for activation of peripheral immunity; we will analyze B and T cell activation-specific cell surface markers (CD19, B220, CD40, CD27, CD28, CD30, CD37, CD38, CD43, and surface IgG, IgM, and IgD; CD4, CD8, HLA-DR, CD11b, CD25, CD38, CD45RO, CD134, CD150, CRTAM, FOXP3, Ly-m22 by FACS), transcription (AID, I κ B α ; granzyme, perforin, HLA-DRA by RT-PCR) and secreted cytokines (IgG, IgM; sIL2R, neopterin, sCD4, sCD8, TNF α , IL-1b, IL-2, IL-6 by ELISA) before and after irradiation. To this end, an additional 10 cc of peripheral blood will be collected after the LEAD RT treatment at about 24 hr. (\pm 12 hr.) following the procedure. One tube of whole blood from patients will be collected into an anticoagulant tube (EDTA). Buffy coat and plasma will be isolated by centrifugation. Plasma will be frozen at -80°C until analysis. PBMCs will be isolated from buffy coat on a ficoll gradient and frozen in RPMI (+40% FBS, 10% DMSO) until analysis. The second tube will be the 7-mL Vacutainer SST Gel & Clot Activator Plus Plastic (BD). Blood collected tubes will be gently inverted to evenly mix the clot activator and will be kept at room temperature for 1 hr for serum separation and will be shipped to [name] lab for ELISA. The whole blood will be shipped to [name] laboratory. The results of the biomarker confirmation will be correlated with clinical response.

4.13 Proteomic and Genomic Analyses of Blood and Urine

The objectives are 1) to examine protein in pretreatment serum, hypermethylated DNA in urine for patterns that predict for biochemical failure and 2) to determine if the profiles from serum and urine in men treated with radiotherapy may be used as an adjunct to PSA in identifying failure at an earlier point in time. For the second objective, serum and urine samples will be collected during the last week of RT at 6 weeks, 3 months, at 9 months and within 2 months prior to the 2-year prostate biopsy.

To summarize, we plan to collect plasma and serum, as well as red cells and lymphocytes (buffy coat) before treatment and at the designated follow-up times to determine if the protein changes observed are useful in predicting the outcome of men treated with radiotherapy. We anticipate that the research biosamples will be obtained from all 25 cases. While these are exploratory studies, of key importance is to have such samples collected prospectively on a well-defined group of patients. The project on genomics of urine samples builds on our results with the detection of hypermethylation of the glutathione S-transferase p1 (GSTP1) gene locus in urine.⁹²Promoter hypermethylation is a common mechanism for tumor suppressor inactivation in human cancers and is a promising target for molecular detection of prostate cancer in urine. *GSTP1* hypermethylation is well established as "early," frequent and cancer specific and can be detected by the sensitive MSP test. The hypermethylation of *GSTP1* is found in >90% of primary prostate cancers, but not in normal prostatic tissue or other normal tissues. *GSTP1* was detected in the urine of 79% of men with PC. *GSTP1* and *RAR β* gene hypermethylation in voided urine DNA will be assayed with the aim of 100% diagnostic coverage for molecular detection of recurrent prostate cancer. The diagnostic utility of *GSTP1*

and *RARβ* hypermethylation will be determined. Further genes will be added to the detection panel to provide molecular prognostic information.

4.14 Supportive Care Guidelines

All supportive therapy for optimal medical care will be given during the study period at the discretion of the managing physician(s) within the parameters of the protocol and documented. Most patients have grade 2 or lower urinary or bowel symptoms during and after treatment. Symptoms will be documented at least once a week as part of routine treatment clinic. In very rare cases, patients may experience extreme symptoms, such as urinary obstruction, diarrhea or significant bleeding requiring transfusion. Supportive measures, catheter placement and medication will be instituted as needed. Common supportive medications include:

- Antidiarrheals: Antidiarrheals, such as loperamide hydrochloride or diphenoxylate-atropine, may be used as needed. The amounts of the drug(s) and dates used should be documented as much as possible.
- Antispasmodics: Antispasmodics, such as oxybutynin or tolterodine tartrate, may be used as needed. The amounts of the drug(s) and dates used should be documented as much as possible.
- Alpha Blockers: Alpha blockers, such as doxazosin mesylate, terazosin hydrochloride or tamsulosin hydrochloride may be used as needed. The amounts of the drug(s) and dates used should be documented as much as possible.
- Analgesics: Analgesics is a broad category, including non-narcotic and narcotic agents. The use of non-narcotic agents, such as acetaminophen, non-steroidal anti-inflammatory agents or phenazopyridine hydrochloride for radiotherapy treatment-related pain should be documented as much as possible. Narcotic use as a consequence of treatment should also be recorded.
- Erectile Dysfunction: Erectile dysfunction may be treated with medical management (e.g., phosphodiesterase inhibitors), vacuum pumps or other devices as appropriate. The amounts of the drug(s) used and the dates that medical management or the use of mechanical devices was started should be documented.

4.15 Duration of Therapy

- Within 4 weeks of enrollment, patients will be biopsied (patient may refuse) and fiducial markers placed.
- LHRH agonist androgen deprivation therapy: LHRH agonist therapy may start up to two months prior to signing consent form or any time after signing consent form, up to two weeks after fiducial marker placement (preferred) in men with intermediate or high (optional) risk prostate cancer. All patients may receive 4-6 months (+/- 2 months) LHRH agonist therapy.
- Anti-androgen treatment should begin 1-14 days prior to LHRH agonist injections. Anti-androgen will be continued four 4 months.
- .
- Standard fraction RT: Day 2 of radiotherapy will start within 32 hr of LEAD RT and will consist of 38 fractions at 2.0 Gy over 7.5 weeks
- Treatment will be stopped for grade 4 acute toxicity (according to the current version of Common Terminology Criteria for Adverse Events (CTCAE version 4), but may be resumed per protocol if the treatment break is less than 10 working days. Since we have never observed grade 4 toxicity acutely using IMRT (conformal CyberKnife treatment is an IMRT-like treatment),

such an event is unlikely. If grade 4 toxicity resolves beyond the 10 days the treating physician will decide whether to give additional RT.

- Treatment will be stopped if metastasis is detected by radiographic or pathologic evidence and the patient will be removed from the study, but not from intent-to-treat analysis. A work-up for metastasis during treatment will only be carried out if the treating physician deems necessary.
- Multiparametric MRI exams of the prostate/pelvis will be carried out after RT at 3 months, 9 months, and within 2 months of the post-treatment prostate biopsies.
- Prostate biopsies will be taken at 2-2.5 years post completion of all therapy.

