2.2 Secondary Objectives

- To measure the risk of leaving tumor cells in the prostate after LEAD RT by obtaining serial post-RT MRI's (3 months and 9 months, and within 2 months of the post-treatment prostate biopsy).
- To quantify biomarker expression in different prostate tumor regions, comparing specifically the multiparametric suspicious and unsuspecting regions.
- To determine the proportion of study patients with positive prostate biopsies at 2-2.5 years after completion of therapy as a preliminary indication of the efficacy.
- To report failure-free (biochemical and clinical progression) and overall survival.
- To assess Health-Related Quality of Life (HRQOL) in the study patients.

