5.2 Evaluations During Treatment

- High dose boost will be started on a Monday, Tuesday or Wednesday.
- Plasma and serum (up to 4 tubes) and urine (50 mL) will be collected for research (research fluids) at 24 hr post-LEAD RT and during the last week of RT.
- Weekly history and physical, evaluation of patient's ability to perform daily activities (Zubrod performance status; Karnovsky or ECOG performance status may be used to estimate Zubrod), and evaluation of toxicity.
- Blood (up to 4 tubes) will be drawn at RT completion during the last week of RT from a vein for the following tests:
 - Serum Testosterone.
 - Liver function tests (only if on ADT)
 - Complete cell counts
 - Lipid profile
- Quality of Life surveys will be administered during the last week of RT:
 - The Expanded Prostate Cancer Index Composite Questionnaire-SF12 (EPIC-SF12)
 - Memorial Anxiety Scale for Prostate Cancer patients (MAX-PC)
- International Prostate Symptom Index (IPSS) questionnaire during the last week of RT.

5.3 Post-treatment Evaluations (after RT) *Measurements and follow-up visits should occur ± 2 weeks up to the 3 month visit and ± 4 weeks for subsequent measurements/visits*

- History and physical, evaluation of patient's ability to perform daily activities (Zubrod performance status; Karnovsky or ECOG performance status may be used to estimate Zubrod), and evaluation of side effects at 6 weeks, 3 months, and then every 6 months for 5.25 years.
- Blood work (tubes of blood will be drawn at each follow-up as described below):
 - PSA at 6 weeks, 3 months and then every 6 months for 5.25 years.
 - Testosterone at 6 weeks, 3 months, and 9 months after radiotherapy. If testosterone remains abnormally low after ADT, tests will continue to be done at each follow-up visit.
 - BUN and creatinine to evaluate kidney function prior to MRIs at 3 months, 9 months and within 2 months prior to the 2-year prostate biopsy.
 - Liver function tests at 6 weeks and 3 months after radiotherapy (only at 3 months if not receiving ADT).
 - Complete blood counts at 3 months.
 - Lipid profile at 6 weeks, 3 months, 9 months, and within 2 months prior to the 2-year prostate biopsy.
- Plasma and serum (up to 4 tubes), and urine (50 mL) for research fluid tests will be obtained at 6 weeks, 3 months, 9 months and within 2 months prior to the 2-year prostate biopsy.

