7.1.10 Side effects

- **Lupron**: In the majority of patients testosterone levels increased above baseline during the first week, declining thereafter to baseline levels or below by the end of the second week of treatment. The most common side effect of Leuprolide is vasomotor hot flashes; edema, gynecomastia, bone pain, thrombosis, and GI disturbances have occurred. Potential exacerbations of signs and symptoms during the first few weeks of treatment is a concern in patients with vertebral metastases and/or urinary obstruction or hematuria which, if aggravated, may lead to neurological problems such as temporary weakness and/or paresthesia of the lower limbs or worsening of urinary symptoms

- **Zoladex**: During routine screening of Zoladex, no significant pharmacological activity was apparent in the cardiovascular, respiratory, central nervous, renal, metabolic, coagulation or gastric acid secretory systems. Studies have shown that serum levels of testosterone can be reduced and maintained within the castrate range resulting in objective evidence of tumor regression. Other than the occasional transient worsening of cancer symptoms (tumor flare) due to an initial temporary rise in testosterone serum levels on initiating therapy, no significant toxicity apart from that attributed to castration (hot flashes, decreased erections, impotence) has been reported. In general, allergic reactions have been extremely uncommon with Zoladex therapy. There have been isolated reports of urethral obstruction, urticaria, or spinal cord compression.

- **Casodex**: The drug is well tolerated and has good response rates in phase II trials. Non-pharmacological adverse events, reported in the trial using bicalutamide 50 mg as

monotherapy include asthenia, pelvic pain, peripheral edema, pruritus, rash, constipation, impotence, dyspnea, nausea, and pain.⁹³ There has been no observed change in cardiac parameters during long-term administration of bicalutamide 50 mg daily. When bicalutamide 50 mg was given in combination with an LHRH analogue, the LHRH analogue adverse event profile predominated with a high incidence of hot flashes (49%) and relatively low incidences of gynecomastia (4.7%) and breast pain (3.2%), the associated pharmacological effects of bicalutamide monotherapy.⁹³ Bicalutamide or flutamide is recommended during the first month of LHRH agonist treatment.

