14.2 Analysis Plan

Study findings will include descriptive statistics summarizing patient baseline characteristics, RT planning parameters and treatment received⁹⁴. A detailed safety profile will be provided consisting of lists and tabulations of all adverse events indicating type, grade, attribution to treatment and time of onset relative to treatment according to CTCAE standards. This will be done separately for acute and late toxicity (see Section 9.1). Patient level summaries will include worst grade toxicity and the number and duration of treatment delays attributable to toxicity.

Feasibility will be assessed by reporting the proportion of enrolled patients who are administered LEAD dose following successful MRI-guided planning and corresponding 95% confidence interval (CI) using the exact binomial method. The same method will be used to estimate the two-year positive biopsy rate defined as the proportion of positive biopsy findings among patients without clinical or biochemical failure two years after completing study treatment.

Clinical outcome will be further assessed by estimating the rate of biochemical failure, as defined in Section 9.1, using the method of cumulative incidence allowing for competing risk of death without biochemical failure. Biochemical failure free survival will be estimated by the Kaplan Meier method. Similar analysis will be provided for the combined rate of biochemical and clinical failure (cumulative incidence) and failure free survival (Kaplan Meier). Although death of study patients during the planned follow up period is expected to be rare and not attributable to prostate cancer, we include these survival endpoints (biochemical failure-free, failure-free, and overall survival) for completeness.

We will summarize the scores of QOL assessments with descriptive statistics and apply mixed effects modeling to evaluate changes over time.

Finally, to the extent permitted by available data from baseline biopsies, exploratory analysis will be performed to investigate the relationship between the level of biomarker expression in tumor tissue within vs. outside the DCE-MRI determined region and the correlation between these measures and Gleason score. Analysis of the sequential imaging studies will correlate the presence/absence of DCE enhancing area and its volume with biopsy positivity at 2 – 2.5 years. We will attempt to establish the ability of MRI for early assessment of RT outcome.

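### The 3- and 9-month MRI findings are used without regard to ADT, so the 3-month picture of residual tumor, and its correlation with the later biopsy, can be confounded by hormone exposure

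*Combined protocol and SAP*

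**What the plan says.** The first secondary objective in section 2.2 is "To measure the risk of leaving tumor cells in the prostate after LEAD RT by obtaining serial post-RT MRI's", at 3 months, 9 months and close to the post-treatment biopsy. Section 4.15 sets the clock: "Multiparametric MRI exams of the prostate/pelvis will be carried out after RT at 3 months, 9 months", followed by a third scan within two months of the biopsy.

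On hormone therapy the same section says "All patients may receive 4-6 months (+/- 2 months) LHRH agonist therapy". On its start it says "LHRH agonist therapy may start up to two months prior to signing consent form or any time after signing consent form", with two weeks after fiducial placement as the latest point. Section 3.1 D leaves ADT to the treating physician and does not require it. Section 3.2 D excludes more than 8 months.

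The biopsy runs on a different clock. Section 8.0 and footnote c of Appendix I count its 2–2.5 years from the end of RT or of ADT, taking the later.

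The only imaging analysis in section 14.2 is to "correlate the presence/absence of DCE enhancing area and its volume with biopsy positivity" at 2–2.5 years, in order to learn whether MRI can assess RT outcome early. No ADT grouping, covariate or testosterone term appears there, and section 14.3 (stratification) is N/A.

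Two further passages matter. Section 5.3 schedules "Testosterone at 6 weeks, 3 months, and 9 months after radiotherapy", so testosterone is drawn at both early MRI visits. Section 7.1.10 says of goserelin that testosterone can be lowered and "maintained within the castrate range resulting in objective evidence of tumor regression".

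**The concern.** If LHRH therapy itself shrinks tumor, an early scan taken under or shortly after it shows the combined effect of hormones and radiation. The scan of a man who never had ADT shows radiation alone. Pooling the two has two consequences.

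- Any residual-enhancement rate drawn from the 3-month scans to serve objective 2.2 depends on how many men happened to take ADT and when. A Phase II trial with a different ADT mix could not use it as a reference.
- In the MRI–biopsy correlation, ADT may affect both variables. A pooled association could then appear where MRI carries no information, or a real one could be masked. ADT use is also tied to risk group (section 4.7), which may push the other way, so the direction of the bias cannot be settled in advance.

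The plan makes the biopsy wait for ADT to end but does not do the same for the early scans correlated with it.

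**Working it through.** The plan gives no figure to reproduce on this point. The check is a timeline followed by two illustrations.

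**Inputs from the protocol**
- LHRH duration: 4−2 = 2 months to 6+2 = 8 months (sections 4.15 and 3.2 D).
- LHRH start, *s*: from 2 months (8.7 weeks) before consent to fiducial week + 2 (section 4.15).
- Fiducial placement, *F*: 0 to 4 weeks after enrollment (section 4.15), with consent taken as week 0.
- RT length: 7.5 weeks (section 4.15; 38 fractions at 5 per week give 7.6).
- Scan windows, *w*: ±2 weeks at 3 months, ±4 weeks at 9 months (section 5.3).

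**Assumption.** Gap *g* from fiducial placement to RT is 1 to 8 weeks. Section 4.6 gives only the 1-week minimum before the planning MRI.

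**Formula.** With one month = 4.348 weeks, *m* the scan month and *d* the LHRH months, weeks since the end of LHRH coverage = *F* + *g* + 7.5 + 4.348*m* + *w* − (*s* + 4.348*d*). A negative value means still covered.

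**3-month scan**
- Most still to run (*F* = 0, *g* = 1, *s* = 2, *d* = 8, *w* = −2): 0 + 1 + 7.5 + 13.04 − 2 − (2 + 34.79) = −17.2 weeks.
- Longest off (*F* = 4, *g* = 8, *s* = −8.7, *d* = 2, *w* = +2): 4 + 8 + 7.5 + 13.04 + 2 − (−8.70 + 8.70) = 34.5 weeks.
- With 4- and 6-month courses only, the range is −8.5 to 25.8 weeks.
- Worked case (*F* = 4, *g* = 4, *s* = 6, scan on time): 28.54 − 6 − 4.348*d*. A 4-month course ended 5.2 weeks earlier; a 6-month course has 3.5 weeks left; an 8-month course has 12.2 weeks left.

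**9-month scan**
- Shortest time off (*F* = 0, *g* = 1, *s* = 2, *d* = 8, *w* = −4): 0 + 1 + 7.5 + 39.13 − 4 − (2 + 34.79) = 6.8 weeks. With a 6-month course it is 15.5 weeks. The longest is 62.6 weeks.
- Nobody on schedule is still covered, although section 5.3 foresees testosterone staying low after ADT.

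**Scan near the biopsy.** The biopsy is at least 24 months past RT or ADT and the scan is within 2 months of it, so at least about 22 months past ADT. A biopsy brought forward for suspected failure (Appendix I, footnote c) is the exception.

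**Illustration 1: pooled rate (assumed rates).** If a share *f* of men is ADT-affected and ADT raises MRI clearance by *δ*, the pooled rate shifts by *f* × *δ*. For *f* 0.25–0.75 and *δ* 0.10–0.30 this is 0.25 × 0.10 = 2.5 points to 0.75 × 0.30 = 22.5 points. For example, with residual enhancement of 40% without ADT and 15% with it, the pooled rate is 0.7 × 40 + 0.3 × 15 = 32.5% if 30% take ADT, and 0.3 × 40 + 0.7 × 15 = 22.5% if 70% do. The radiation effect is the same in both.

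**Illustration 2: pooled odds ratio (assumed rates).** Half the men take ADT, and MRI and biopsy are independent within each group.
- ADT lowers enhancement from 50% to 20% and biopsy positivity from 50% to 25%. The cell probabilities are both positive 0.15, both negative 0.425, MRI only 0.20, biopsy only 0.225. OR = (0.15 × 0.425)/(0.20 × 0.225) = 1.42.
- ADT lowers enhancement from 60% to 10% and positivity from 50% to 20%: OR = (0.16 × 0.46)/(0.19 × 0.19) = 2.04.
- The true odds ratio within each group is 1.

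**The case against.** Several points on the other side stand.

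- A reader might infer that the plan will report ADT-induced regression as a LEAD effect. The documents do not say that. Section 14.2 speaks of RT outcome, and in objective 2.2 the reference to LEAD can be read as one of time. The stated preliminary efficacy indicator is the biopsy.
- A reader might infer that splitting by ADT would isolate LEAD. It would not. Every man also receives 76 Gy IMRT and there is no control arm.
- A reader might infer that men could still be on LHRH at 9 months. The 8-month cap and the timeline rule that out.
- The document support is limited. Section 7.1.10 speaks of tumor regression in general and not of DCE enhancement. The sentence on organ atrophy in section 7.1.3 appears with animal findings and is not relied on here.
- All rates in the illustrations are assumed, and sampling noise is large beside them. With 25 men contributing both results, approximate 95% intervals are 0.26–7.6 around 1.42 and 0.37–11.2 around 2.04. Biopsies may be refused, so fewer may contribute.
- The analysis is exploratory. It feeds neither the primary objective (section 2.1) nor any stopping rule (section 14.4).

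These points limit the claim and its weight without removing it. Small numbers are no reason to leave a foreseeable common cause untabulated. Summarizing treatment received, as section 14.2 plans, does not link it to the scans.

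**Conclusion.** The point holds in a limited form. At the 3-month MRI, men may be on, recently off, long off or never on LHRH therapy. At 9 months they are off by about 7 weeks or more, possibly with testosterone still low, or never treated. Neither objective 2.2 nor section 14.2 takes account of this, so the pooled 3-month enhancement rate depends on the ADT mix and the pooled MRI–biopsy correlation can be confounded. The problem is mainly at 3 months; the scan near the biopsy is largely free of it.

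The spread in exposure follows from the protocol's own limits plus the assumed 1- to 8-week gap to RT. The size of the bias (2.5 to 22.5 points; spurious odds ratios of 1.4 to 2.0) rests wholly on assumed rates and shows what is possible, not what is expected. This is worth correcting because the correction is cheap and the results are meant to inform Phase II. It does not threaten the trial's primary conclusions.

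**What to change.** In section 14.2:

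- Tabulate enhancement (presence and volume) at 3 and 9 months by ADT use, none versus any. List for each man the time since last LHRH coverage and the same-visit testosterone.
- Show the MRI–biopsy cross-tabulation by ADT use, or an ADT-stratified exact estimate, beside the pooled result, and label it descriptive.
- Flag baseline MRIs taken after LHRH start. This can happen because the scan may be up to 3 months before entry (section 5.1) and LHRH up to 2 months before consent.
- State that MRI change reflects LEAD plus 76 Gy IMRT with or without ADT and cannot be attributed to LEAD alone.

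A finer split (never, on, off) at each scan with no pooled result is not workable with 25 men.

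The cost is a few lines of text and one descriptive table, with no new visits, tests or patients. Testosterone is already drawn, and the end of ADT is already needed to date the biopsy. The eligibility checklist records only planned months and whether ADT began within two months of consent, so the case report form should be confirmed to hold the actual LHRH dates and depot lengths. Within-group intervals will be wide: 6 of 12 has an exact 95% interval of 21% to 79%, against 28% to 69% for 12 of 25. A two-way split also leaves the link between ADT and risk group unadjusted, which the text should say.
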